At the Children’s Hospital at Montefiore (CHAM), the macrolide azithromycin is currently being used by some practitioners for its presumed anti-inflammatory effects in patients with acute asthma exacerbations. In 2010, 14% of 895 pediatric patients with a primary diagnosis of asthma received azithromycin during their inpatient stay. (Data obtained from a Clinical Looking Glass preliminary search). The length of stay of patients who received azithromycin was longer (mean: 4.5 days, median 3.8 days) than those who did not receive azithromycin (mean: 3.2 days, median 2 days) which may suggest that the current practice includes administering azithromycin to more severe asthma patients or patients refractory to standard treatments. A similar search of patients admitted with a primary diagnosis of asthma from 2008-2010 and transferred at any time to a pediatric intensive care bed, revealed that even more received azithromycin – over 30%. However, the length of stay for the critical care patients was unchanged whether they received azithromycin or not (both groups had a mean: 5.0 days, and median: 4.0 days). Although currently 14-30% of children admitted with acute asthma to CHAM receive azithromycin, there is currently no evidence on the efficacy of this treatment practice.

We propose to conduct the first double-blind, randomized, placebo-controlled trial to determine whether azithromycin will effect inpatient length of stay in children with acute asthma exacerbations.

OBJECTIVES

Primary Objective:

To conduct a double-blind, randomized, placebo-controlled trial to determine the clinical efficacy of azithromycin treatment in hospitalized children with acute asthma exacerbations, as measured by length of stay.

Secondary Objectives in a Subset of Patients – “Mechanism Subset Study”:

1. To quantify the relative prevalence of atypical infection in the inpatient pediatric asthma population.
2. To determine if atypical infection with *Mycoplasma pneumoniae* or *Chlamydia pneumoniae* is associated with treatment effect, if found.
3. To determine immunomodulatory effects of azithromycin in children hospitalized with acute asthma exacerbations, as measured by neutrophil counts, eosinophil counts, and interleukin-8.

Hypothesis:

Azithromycin treatment will decrease length of stay in children with persistent asthma hospitalized with acute asthma exacerbation.

OUTCOME MEASURES

Primary Outcome:

Length of Stay

Secondary Outcomes:

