4. Diagnosis of infection requiring antibiotics during the 3-day course of azithromycin/placebo. (However, if the diagnosis of infection and initiation of antibiotics is after the

completion of the 3-day course of azithromycin/placebo, the antibiotic will be recorded and reported. Patients given antibiotics after the completion of the 3-day course of study drug will not be withdrawn from the study and their outcomes will be included in analysis.)

Safety Exit Criteria: Worsening of clinical status requiring invasive or non-invasive ventilatory support

Study Design

This is a double-blind, randomized, placebo-controlled trial. Patients between the ages of 4-12 years of age admitted to the Children's Hospital at Montefiore (CHAM) with an admission diagnosis of asthma exacerbation, as determined by the admitting physician, will be assessed for eligibility within 12 hours of admission by study personnel. Patients may be enrolled in the pediatric emergency room, pediatric inpatient units, or pediatric intensive care unit.

Potential study patients will be identified by the pediatric emergency room staff, pediatric housestaff who will page the research pager upon admission. In addition, attending physicians in the emergency room, pediatric units, and pediatric intensive care unit can refer patients by paging the research paper. Study personnel will review with primary care team any studies (including chest x-ray) that may alter the decision to start antibiotics prior to enrollment in the study. A member of the medical team caring for the patient will approach the parent/guardian and inquire if study personnel can discuss the study with him/her. If a parent/guardian is not available, the research personnel will return when one is available. If the parent/guardian agrees, study personnel will approach him/her and complete a standardized interview to determine if the patient meets eligibility requirements (see Eligibility Questionnaire). If eligibility requirements are met, the research personnel will obtain informed consent from the parent/guardian and assent from the child (if applicable) for participation in the study. If a female patient has achieved menarche, a pregnancy test will be administered with the consent of the parent/guardian and assent of the patient. Pregnant patients will be excluded from the study.

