The data from the interview questionnaire will be coded and descriptive statistics will be used to analyze the baseline characteristics of the two groups. If the parent characteristics are not balanced, multi-variable analysis will be utilized to adjust for variables not balanced by randomization. Secondary outcome measures will be compared using chi-squared test for categorical data and t-test or Mann-Whitney U test for continuous data, with statistical significance considered a p value < 0.05.

Due to the invasive nature of the sample collection in the "Mechanism Subset Study", only 25% of patients are expected to agree to submit to this portion of the study. These patients may not be representative of all patients in each arm of the study and will not be randomized. This subset study will be a pilot and feasibility study for future investigation into the potential mechanism of action of azithromycin in asthma. Data will be analyzed to compare the proportion of positive lab findings in each group using chi-squared analysis. There will not likely be sufficient power to find statistical significance, but the results will be used to estimate the effect size for subsequent study.

ETHICAL CONSIDERATIONS

Risks/Benefits

The potential risks are considered minimal. This study meets the category in the U.S. Department of Health and Human Services Code of Federal Regulations, Part 46, Subpart D (§46.405) for research involving greater than minimal risk but presenting the prospect of direct benefit to the individual subjects. The risks are deemed by the investigators to be justified by the anticipated benefit to the subjects; and the anticipated benefit is at least as favorable to the subjects as that presented by available alternative approaches.

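### Mechanism subset (minor): the stated analysis does not answer objective 2, makes no use of the enrolment marker value, and does not note that the second sample depends on length of stay

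*Combined protocol and SAP*

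**What the plan says.** **Objectives.** The primary objective concerns "clinical efficacy of azithromycin treatment in hospitalized children with acute asthma exacerbations, as measured by length of stay". Secondary objective 2 asks whether atypical infection "is associated with treatment effect, if found". Secondary objective 3 reads: "To determine immunomodulatory effects of azithromycin in children hospitalized with acute asthma exacerbations, as measured by neutrophil counts, eosinophil counts, and interleukin-8".

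**Methods, Mechanism Subset Study.** Blood and nasal aspirate are taken at enrolment and again on the calendar day 48 hours later, and the section gives baseline against post-treatment comparison as the reason for two samples. A failed first blood draw does not rule out the second. A child who goes home before 48 hours, or for whom no research staff are available, has no second set.

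**Statistical Analysis.** The only subset-specific method is: "Data will be analyzed to compare the proportion of positive lab findings in each group using chi-squared analysis". The general rule is: "Secondary outcome measures will be compared using chi-squared test for categorical data and t-test or Mann-Whitney U test for continuous data". Multivariable adjustment is foreseen only for characteristics found to be unbalanced. On the subset the plan adds: "These patients may not be representative of all patients in each arm of the study and will not be randomized". It expects low power and says that "the results will be used to estimate the effect size for subsequent study".

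**The concern.** Three gaps sit together.

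1. Objective 2 is a question of effect modification. A chi-squared test of positivity by arm is a different question. Applied to enrolment samples it compares arms before treatment; applied to 48-hour samples it asks about clearance. The plan does not say which, and neither shows whether the effect on stay differs between infected and uninfected children.
2. For counts and IL-8, the t-test or Mann-Whitney rule does not say whether 48-hour values or changes are compared, and no stated analysis uses the enrolment value.
3. The plan's caveat on representativeness follows from consent to invasive sampling. Consent is sought around enrolment under blinding, so it mainly limits generalisation. Discharge before 48 hours happens after treatment starts. If azithromycin shortens stay, it removes more second samples from its own arm, and that affects the comparison between arms.

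At stake is the subset's stated product, an effect size for a later study. As written, objective 2 has no planned estimate even if an effect is found, the marker estimate is left to later choice, and its conditioning on continued hospital stay would go unreported.

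**Working it through.** **Inputs from the Statistical Analysis section:** mean stay 3.0 d, median 2.5 d, SD 1.6 d; target difference 0.67 d; 96 evaluable and 107 enrolled per group; 25% subset uptake. **From Background:** prevalence of atypical infection 18-56%. **From Study Design:** a child "will be assessed for eligibility within 12 hours of admission by study personnel". **Assumed, not in the documents:** the cut-off for having a second sample, the marker correlations, and that the 2011 stay figures and the prevalence range apply to enrolled children.

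**The plan's own figures.** A two-sample t-test (0.67 d, SD 1.6, two-sided 0.05, 80% power) needs 90.5, so 91 per group. Dividing by the Mann-Whitney relative efficiency gives 90.5 x 9/pi^2 = 82.5, so 83 (logistic); 91 (uniform); and 91 x pi/3 = 95.3, so 96 (normal). 96/0.90 = 106.7, so 107. The stated 83-96 and 107 reproduce.

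**Subset size.** 0.25 x 192 = 48 and 0.25 x 214 = 53.5, so 24-27 per arm.

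**Objective 2.** With n per arm and a proportion p infected, the interaction on stay has SE = 1.6 x sqrt(2/(np) + 2/(n(1-p))).
- n = 24: 1.20 d at p = 0.18 and 0.93 d at p = 0.56.
- n = 26.75: 1.14 d and 0.88 d.
- 95% half-width = 1.96 x SE = 1.73-2.36 d, which is 2.6-3.5 times 0.67 d.

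An estimate can be given, but it can only be exploratory.

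**Enrolment value.** With enrolment-second correlation r, variance relative to comparing 48-hour values is 1 - r^2 for ANCOVA and 2(1 - r) for a change score. At r = 0.3, 0.5 and 0.7 these are 0.91, 0.75, 0.51 and 1.4, 1.0, 0.6. ANCOVA lowers variance by 9-49%; a change score raises it by 40%, leaves it unchanged, or lowers it by 40%.

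**Second-sample availability.** The cut-off is taken as 48 h plus 0-12 h, so 2.0-2.5 d after admission. The effect on stay is either a constant shift (stay minus 0.67 d) or proportional (stay x 2.33/3.0). For the one shape below that matches all three stay figures, 1.4 + exponential with mean 1.6, P(stay > 2.0) on placebo is exp(-0.6/1.6) = 0.687, and with the constant shift exp(-1.27/1.6) = 0.452.

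| Shape (mean 3.0 d) | >2.0 d: placebo | constant | proportional | >2.5 d: placebo | constant | proportional |
|---|---|---|---|---|---|---|
| Normal, SD 1.6 | 0.734 | 0.582 | 0.605 | 0.623 | 0.458 | 0.446 |
| Lognormal, SD 1.6 | 0.712 | 0.493 | 0.522 | 0.545 | 0.359 | 0.348 |
| Gamma, SD 1.6 | 0.701 | 0.514 | 0.539 | 0.560 | 0.389 | 0.378 |
| Shifted exponential | 0.687 | 0.452 | 0.480 | 0.503 | 0.331 | 0.321 |
| Lognormal, median 2.5 | 0.644 | 0.457 | 0.480 | 0.500 | 0.347 | 0.338 |

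The gap between arms is 15-24 points with a constant shift and 13-21 with a proportional effect, so 13-24 overall. If calendar-day timing moves the cut-off to 1.5 d, the ranges are 13-32 and 8-22, so 8-32 overall.

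**Shift in the marker comparison.** This was simulated with no true marker effect, a constant 0.67 d shift, enrolment-second correlation 0.5 and marker-stay correlation 0.3-0.5, at the 2.0-2.5 d cut-off.
- Unadjusted: 0.07-0.18 SD.
- Enrolment value equally correlated with stay: ANCOVA leaves about 0.04-0.10 SD; a change score leaves essentially none.
- Enrolment value unrelated to stay: neither lowers it.

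With a positive marker-stay correlation, the azithromycin arm appears higher on the marker; with a negative one, lower.

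**Pilot precision.** With 12.0-19.6 placebo and 7.9-15.6 azithromycin children sampled twice, SE = sqrt(1/n0 + 1/n1) = 0.34-0.46 SD.

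**The case against.** The plan is candid about what this subset is. It calls it a pilot, expects too little power, warns that volunteers may be unrepresentative, and states the discharge rule openly. Objective 2 applies only if an effect is found, and the interaction would be too imprecise to settle anything. The intention to compare baseline with post-treatment samples is on record, and the general rule can be read to cover counts and IL-8. All of this stands, and it keeps the point minor. It does not supply a method for objective 2 or say how the enrolment value enters.

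The size of the discharge effect also deserves caution. It needs the full 0.67 d effect; with half of it (normal stay, 2.0-2.5 d cut-off) the shift is about 0.03-0.06 SD. The stay figures come from 2011 admissions given inhaled steroids, whereas the trial excludes children already on four-hourly albuterol at enrolment. The 12-hour window governs eligibility assessment, not the first sample. These objections stand, so the bias figures are illustrative only.

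A reader might infer that ANCOVA cures the discharge problem. It does not: where the enrolment value is as correlated with stay as the second value, ANCOVA only roughly halves the shift while a change score removes it; where it is unrelated to stay, neither helps. The case for ANCOVA is precision, and it must deal with children who have no first sample.

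**Conclusion.** The point holds as a minor one. That objective 2 has no analysis, that no stated test uses the enrolment value, and that the plan nowhere links second-sample loss to length of stay are matters of text and need no assumptions. The sizes do need them. The availability gap of 13-24 points (8-32 at 1.5 d) assumes the full 0.67 d effect, the 2011 stay figures and the cut-off. The 0.07-0.18 SD shift further assumes a constant shift in stay and marker-stay correlations of 0.3-0.5, and it lies below the pilot's standard error of 0.34-0.46 SD. The variance reduction of 9-49% assumes an enrolment-second correlation of 0.3-0.7.

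Two stronger readings are not supported. A reader might infer that the mechanism results would be seriously biased; the documents give no marker-stay correlation, and the illustrated shift is small beside the sampling error. A reader might also infer that the trial's main result is at risk; length of stay does not depend on the second sample, so the primary analysis is unaffected.

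**What to change.** Amend the subset paragraph of the Statistical Analysis section.

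(a) For neutrophil and eosinophil counts and IL-8, replace the unadjusted comparison with ANCOVA of the second value on arm and enrolment value, on a log scale where suitable, and report the estimate with its 95% CI. State how zeros and missing first samples are handled. A change-score analysis may be shown as a sensitivity analysis.

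(b) For objective 2, model length of stay on arm, enrolment infection status and their interaction, naming the tests that define a positive status. Report the estimate and CI as exploratory, with no claim of significance.

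(c) Report second-sample availability by arm, separating discharge from staff unavailability, and state that the 48-hour comparison is conditional on still being in hospital.

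The cost is wording and a little analysis time. No sample, visit or patient is added and sampling times do not change. The small downside of (a) is that children without a first sample are lost or need a stated rule.
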